# 5.6 Duration of Therapy

Patients will receive protocol therapy unless:

- 5.6.1 Extraordinary Medical Circumstances: If at any time the constraints of this protocol are detrimental to the patient's health, protocol treatment should be discontinued. In this event submit forms according to the instructions in the E7208 Forms Packet.
- 5.6.2 Patient withdraws consent.
- 5.6.3 Patients should be treated on study with medications as assigned until discontinuation for toxicity or disease progression by RECIST criteria.
- 5.7 Duration of Follow-up

For this protocol, all patients, including those who discontinue protocol therapy early, will be followed for response until progression, even if non-protocol therapy is initiated, and for survival for 5 years from the date of registration. All patients must also be followed through completion of all protocol therapy.

# 6. Measurement of Effect

6.1 Antitumor Effect – Solid Tumors

For the purposes of this study, patients should be re-evaluated for response every eight weeks.

Response and progression will be evaluated in this study using the international criteria proposed by the revised Response Evaluation Criteria in Solid Tumors (RECIST) guideline (version 1.1) [*Eur J Ca* 45:228-247, 2009]. Changes in the largest diameter (unidimensional measurement) of the tumor lesions and the shortest diameter in the case of malignant lymph nodes are used in RECIST.

- The following general principles must be followed:
  - 1. To assess objective response, it is necessary to estimate the overall tumor burden at baseline to which subsequent measurements will be compared. All baseline evaluations should be performed as closely as possible to the beginning of treatment and **never more than four weeks** before registration.
  - 2. Measurable disease is defined by the presence of at least one measurable lesion.
  - 3. All measurements should be recorded in metric notation by use of a ruler or calipers.
  - 4. The same method of assessment and the same technique must be used to characterize each identified lesion at baseline and during follow-up.

# 6.1.1 **Definitions**

# Evaluable for Objective Response

Only those patients who have measurable disease present at baseline, have received at least one cycle of therapy, and have had their disease re-evaluated will be considered evaluable for response. These patients will have their response classified according to the definitions stated below.

(NOTE: Patients who exhibit objective disease progression prior to the end of cycle 1 will also be considered evaluable.)

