## 1.6 Summary of Toxicity Review

The study was closed to accrual on June 14, 2012 after 35 registrations were accrued as per pre-planned toxicity review. 18 patients (17 treated: one case never started assigned therapy) were accrued to Arm A (IC) and 17 (16 treated: one case was a duplicate registration) to Arm B (ICR). AdEERS Reporting was reviewed and real time data were obtained on all treated patients. It was clear that more toxicity was seen in Arm B. Worst toxicity per patient is seen in the figure below. The overall grade 3-5 toxicity rates were 17% for Arm A and 75% for Arm B. There were 2 toxic deaths in Arm B. Toxicities of higher incidence in Arm B included neutropenia, mucositis, diarrhea and GI perforation (including peri-anal abscess). In addition mean dose given in Arm B (mean % RDI) was considerably lower in Arm B: 65% for irinotecan, 85% for cetuximab and 92% for ramucirumab (even though no dose reductions were allowed in the protocol). This compares to 99% irinotecan and 98% cetuximab average %RDI in Arm A. Furthermore, only 3/17 patients in Arm A required dose reduction, compared to 15/16 in Arm B. On the other hand with a median of 8 cycles preliminary analysis showed that fewer patients in Arm B went off treatment for progression compared with Arm A, and more remained on treatment at the time of the analysis. Of the 17 treated in Arm A, 8 out of 9 patients off study had progression (PD), while in Arm B, of the 16 treated, only 1 out of 5 who went off study, went off for PD. These findings suggest potential benefit for the addition of ramucirumab among patients who can tolerate therapy. Therefore, we propose a reduced dose regimen in Arm C (modified ICR) with irinotecan 150 mg/m^2, cetuximab 400  $mq/m^2$  and ramucirumab 6  $mq/m^2$  as starting doses, more strict eligibility criteria, and more aggressive dose modifications for toxicity. Because those patients on protocol who did tolerate the ICR regimen at the reduced doses seemed to stay on study longer, we believe the study should be continued as modified at those lower doses. The Arm C starting doses are equal to the actual "percent recommended dose intensity" received by patients in Arm B.

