# 6.1.4.4 Evaluation of Best Overall Response

The best overall response is the best response recorded from the start of the treatment until disease progression/recurrence or non-protocol therapy (taking as reference for progressive disease the smallest measurements recorded since the treatment started). The patient's best response assignment will depend on the achievement of both measurement and confirmation criteria.

Target Lesions	Non-Target Lesions	New Lesions*	Best Overall Response	Remarks
CR	CR	No	CR	
CR	Non-CR/Non-PD	No	PR	
CR	Not evaluated	No	PR	
PR	Non-PD/not evaluated	No	PR	
SD	Non-PD/not evaluated	No	SD	Documented at least once ≥ 8 wks. from study entry
PD	Any	Yes or No	PD	
Any	PD**	Yes or No	PD	No prior SD, PR or CR
Any	Any	Yes	PD	

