#### Primary Efficacy Design

Patients will be randomized equally between the two treatment arms A (IC) and C (mICR) with stratification based on performance status (0 vs. 1), discontinuation of oxaliplatin before disease progression (Yes vs. No), and time frame of progression (within 6 months of last treatment vs. > 6 months since last treatment). Patients previously randomized to arms A and B before the redesign of the experimental regimen will not be part of the formal efficacy evaluation and will be reported separately.

With 48 eligible patients per arm followed for progression-free survival (disease progression or death without evidence of progression), this study has over 85% power to detect a difference of 4.5 months median PFS in the control arm A (40% PFS at 6 months assuming exponential failure) versus 7.65 months median PFS (58% PFS at 6 months) in the experimental arm (Arm C) using a one-sided stratified log rank test conducted with 15% type 1 error. The study will require approximately 10 months of accrual at 10 patients per month and 6 additional months of follow-up to achieve the events required (67 PFS events) to provide at least 85% power for the stated alternative of a 48% increase in median PFS. Response, overall survival, and toxicity are secondary endpoints and will be reported at the time of primary PFS analysis. With 48 eligible patients per arm, the width of any 90% confidence interval on a binomial proportion will be no wider than 26 percentage points. In addition, the probability of observing a rare (2% probability) toxicity in either arm is greater than 62% at full accrual. Allowing for roughly 5% ineligibility and including the 35 patients who were previously randomized to Arms A and B of the study prior to its redesign, this study will require a total of 135 patients and 100 patients will be accrued to the revised study (Arm A versus Arm C).

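### The evaluable-for-response rule in Section 6.1.1 drops early deaths and patients never re-imaged, conflicts with the 48-patient basis in Section 9.1, and can inflate the response rate

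*Combined protocol and SAP*

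**What the plan says.** Response rate is a named objective (Section 2.2) and a secondary endpoint with no planned test: "Response, overall survival, and toxicity are secondary endpoints and will be reported at the time of primary PFS analysis" (Section 9.1, Primary Efficacy Design).

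The only rule on who counts for response is in Section 6.1.1. Beyond measurable disease at baseline, which eligibility criterion 3.1.4 already requires, patients must "have received at least one cycle of therapy, and have had their disease re-evaluated will be considered evaluable for response". One exception follows: "Patients who exhibit objective disease progression prior to the end of cycle 1 will also be considered evaluable". Under Section 6.1, "patients should be re-evaluated for response every eight weeks", which is four 14-day cycles.

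Three other passages bear on the point:

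- Section 5.7 (Duration of Follow-up): "all patients, including those who discontinue protocol therapy early, will be followed for response until progression, even if non-protocol therapy is initiated".
- Section 6.1.4.4: "The best overall response is the best response recorded from the start of the treatment until disease progression/recurrence or non-protocol therapy". The table there has no row for a patient without a post-baseline assessment.
- Section 9.1: "With 48 eligible patients per arm, the width of any 90% confidence interval on a binomial proportion" is stated to be no more than 26 percentage points. Section 9 does not name the denominator of the response rate.

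**The concern.** Both operative filters in Section 6.1.1, receiving a cycle and being re-evaluated, are met or failed after randomization and can depend on treatment. A patient who dies of toxicity before any scan cannot be a recorded responder. Removing that patient shrinks the denominator and leaves the numerator alone. An evaluable-only rate therefore cannot fall below the all-eligible rate, and the excess grows with early loss.

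The trial adds a drug to an active control, and its first phase showed unequal tolerability. Sections 1.6 and 9.1 report 2 toxic deaths among 16 treated in Arm B and none among 17 treated in Arm A. In Arm B "only 1 out of 5 who went off study, went off for PD", which leaves 4 of 16 treated off study without progression, against 1 of 17 in Arm A. If early loss is also unequal between Arms A and C, an evaluable-only comparison would favour the arm with more loss. With the denominator left open, an analyst could follow Section 6.1.1 or Section 9.1 after seeing the data and claim to follow the plan.

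**Working it through.** **Inputs.** 48 eligible patients per arm and the 26-point bound (Section 9.1). Response to irinotecan plus cetuximab of 20% to 23% (Section 1.1.4). Toxic deaths of 2/16 = 12.5% in Arm B (Section 9.1) and 0.77% in the earlier trial of irinotecan plus cetuximab (Section 9.2). Off study without progression: 4/16 = 25% in Arm B and 1/17 = 5.9% in Arm A (Section 1.6). The share of Arm C lost to re-evaluation, d, is not in the documents; I assume 0% to 25%.

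**Step 1: reproduce the plan's precision figures.** I took the exact (Clopper-Pearson) 90% interval and maximised its width over the number of responders.

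| n | Maximum width (points) | Plan's figure |
|---|---|---|
| 16 | 44.3 | 44.3 |
| 70 | 20.8 | 21 |
| 48 | 25.3 | 26 |

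The method matches the plan at all three sizes.

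**Step 2: apply the bound to a reduced set.**

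| Dropped from 48 | n | Maximum width (points) | Within 26? |
|---|---|---|---|
| 2 | 46 | 25.8 | yes |
| 3 | 45 | 26.1 | no |
| 4 | 44 | 26.4 | no |
| 6 | 42 | 27.1 | no |
| 12 | 36 | 29.3 | no |

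The Section 9.1 figure fits all eligible patients. It stops holding under the Section 6.1.1 set once three or more are lost.

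**Step 3: inflation within an arm.** If the excluded patients have no recorded response, then evaluable rate = p / (1 - d) and inflation = p / (1 - d) - p, where p is the rate among all eligible patients.

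| d | Inflation at p = 20% | Inflation at p = 23% |
|---|---|---|
| 0% | 0 | 0 |
| 0.77% | 0.2 | 0.2 |
| 5% | 1.1 | 1.2 |
| 12.5% | 2.9 | 3.3 |
| 25% | 6.7 | 7.7 |

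Example: 0.20 / 0.875 = 22.9%, so 2.9 points. The 12.5% row assumes that Arm C repeats the Arm B toxic-death share and that every such death precedes re-evaluation. The 25% row assumes that every Arm B exit without progression was early and never followed by a scan. It is an upper bound.

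**Step 4: in whole patients.** Ten responders of 48 is 20.8% (90% CI 11.8 to 32.8). The same ten give 10/46 = 21.7% with 2 dropped, 10/42 = 23.8% (13.5 to 37.0) with 6 dropped, and 10/36 = 27.8% (15.9 to 42.5) with 12 dropped. With all eligible patients as denominator the rate stays at 20.8% whatever the number not re-imaged.

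**Step 5: between arms.** With a true rate of 20% in both arms, loss of 0.77% in Arm A and 12.5% in Arm C gives 22.9% - 20.2% = 2.7 points in favour of Arm C. Loss of 0.77% and 25% gives 26.7% - 20.2% = 6.5 points. Equal loss gives no difference.

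**The case against.** **Section 6.1.1 says whose response is classified, not what the rate is divided by.** This is correct. The one numerical statement that covers response, in Section 9.1, points to all eligible patients. But Section 9.1 neither names the denominator nor says that it replaces the earlier rule, so Section 6.1.1 remains the only explicit rule.

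**A reader might infer that anyone who stops early for toxicity drops out.** The documents do not support this. Section 5.7 requires response follow-up until progression after early discontinuation, and Section 5.4.1(d) keeps a patient on study when one agent is stopped for toxicity. Section 6.1.1 asks for one cycle and a re-evaluation, not eight weeks of tolerated treatment. Section 6.1.4.4 closes the best-response window at non-protocol therapy, but that does not remove a patient from the evaluable set.

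**A reader might infer from Arm B that Arm C will lose more patients before the first scan.** Section 1.6 gives no timing for the Arm B deaths or exits and mentions a median of 8 cycles, about 16 weeks or two scheduled scans. Arm B is outside the formal efficacy comparison. Arm C has lower starting doses and stricter eligibility.

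**The 12.5% case sits badly with the plan's own closing rule.** Section 9.1 closes the study on any toxic death in the first 16 Arm C patients. At a true rate of 12.5%, the chance of none in 16 is 0.875^16 = 0.118. The chance of 6 or more in the next 32 is 0.204. The product is about 2.4%. Reaching 6 of 48 through toxic deaths alone is therefore unlikely, although patients who never receive a cycle or are never scanned for other reasons also count.

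**The consequence is limited.** This also stands. Response has no planned test, and the 90% interval at 10/48 is about 21 points wide. PFS counts death as an event and does not use this definition.

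**Conclusion.** The point holds as an unreconciled denominator with a one-directional risk. Section 6.1.1 states a rule that depends on post-randomization events and adds back only early progression. No section counts early deaths or never-re-imaged patients as non-responders. The Section 9.1 precision bound fits 48 eligible patients but not 45 or fewer.

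If the Section 6.1.1 set is the reported denominator, the inflation is 0 points with no loss, about 1 point at 5%, about 3 points at 12.5% and about 7 to 8 points at 25%. These figures assume a true rate of 20 to 23% and no recorded response among those excluded.

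The stronger conclusion, that the plan does inflate response in the ramucirumab arm, is not supported. It needs the evaluable set to be the denominator, which Section 9 does not say. It also needs more early loss in Arm C than in Arm A, which the Arm B record makes plausible but does not establish. The effect is confined to a secondary endpoint; the primary PFS analysis is unaffected. The change should still be made, because response is a named objective and the remedy needs no new data.

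**What to change.** In Section 9.1, state that the response rate in each arm uses all eligible randomized patients, with those lacking a post-baseline disease assessment counted as non-responders. Add a cross-reference in Section 6.1.1 saying that its evaluable set serves a supportive analysis only. Report the evaluable-only rate beside the main one, with the number of non-evaluable patients and the reasons, by arm.

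The cost is a sentence in Section 9.1, the cross-reference and one extra table. No further patients or data collection are needed. Reported response rates may be slightly lower than evaluable-only rates.

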# Evaluable Non-Target Disease Response

Patients who have lesions present at baseline that are evaluable but do not meet the definitions of measurable disease, have received at least one cycle of therapy, and have had their disease re-evaluated will be considered evaluable for non-target lesion assessment. The response assessment is based on the presence, absence, or unequivocal progression of the lesions.

# 6.1.2 **Disease Parameters**

# Measurable Disease

Measurable lesions are defined as those that can be accurately measured in at least one dimension (longest diameter to be recorded) as  $\ge 20$  mm by chest x-ray, as  $\ge 10$  mm with CT scan, or  $\ge 10$  mm

with calipers by clinical exam. All tumor measurements must be recorded in millimeters.

Malignant Lymph Nodes

To be considered pathologically enlarged and measurable, a lymph node must be  $\geq$  15 mm in **short** axis when assessed by CT scan (CT scan slice thickness recommended to be no greater than 5 mm). At baseline and in follow-up, only the **short** axis will be measured and followed.

# Non-measurable Disease

All other lesions (or sites of disease), including small lesions (longest diameter <10 mm or pathological lymph nodes with  $\ge$  10 to < 15 mm short axis), are considered non-measurable disease. Bone lesions, leptomeningeal disease, ascites, pleural/pericardial effusions, lymphangitis cutis/pulmonitis, inflammatory breast disease, and abdominal masses (not followed by CT or MRI), are considered as non-measurable. Non-measurable also includes lesions that are < 20 mm by chest x-ray.

**NOTE:** Cystic lesions that meet the criteria for radiographically defined simple cysts should not be considered as malignant lesions (neither measurable nor non-measurable) since they are, by definition, simple cysts.

'Cystic lesions' thought to represent cystic metastases can be considered as measurable lesions, if they meet the definition of measurability described above. However, if non-cystic lesions are present in the same patient, these are preferred for selection as target lesions.

# Target Lesions

All measurable lesions up to a maximum of 2 lesions per organ and 5 lesions in total, representative of all involved organs, should be identified as target lesions and recorded and measured at baseline. Target lesions should be selected on the basis of their size (lesions with the longest diameter), be representative of all involved organs, but in addition should be those that lend themselves to reproducible repeated measurements. It may be the case that, on occasion, the largest lesion does not lend itself to reproducible measurement in which circumstance the next largest lesion which can be measured reproducibly should be selected.

A sum of the diameters (longest for non-nodal lesions, short axis for nodal lesions) for all target lesions will be calculated and reported as the baseline sum diameters. If lymph nodes are to be included in the sum, then only the short axis is added into the sum. The baseline sum of the diameters will be used as reference to further characterize any objective tumor regression in the measurable dimension of the disease.

# Non-target Lesions

All other lesions (or sites of disease) including any measurable lesions over and above the 5 target lesions should be identified as non-target lesions and should also be recorded at baseline. Measurements of these lesions are not required, but the presence or absence of unequivocal progression of each should be noted throughout followup.

# 6.1.3 Methods for Evaluation of Measurable Disease

All measurements should be taken and recorded in metric notation using a ruler or calipers. All baseline evaluations should be performed as closely as possible to the beginning of treatment and never more than 4 weeks before registration.

The same method of assessment and the same technique must be used to characterize each identified and reported lesion at baseline and during follow-up. Imaging-based evaluation is preferred to evaluation by clinical examination unless the lesion(s) being followed cannot be imaged but are assessable by clinical exam.

# **Clinical Lesions**

Clinical lesions will only be considered measurable when they are superficial (e.g., skin nodules and palpable lymph nodes) and  $\geq 10$  mm in diameter as assessed using calipers (e.g., skin nodules). In the case of skin lesions, documentation by color photography, including a ruler to estimate the size of the lesion, is recommended.

# Chest X-ray

Lesions on chest x-ray are acceptable as measurable lesions when they are clearly defined and surrounded by aerated lung. However, CT is preferable.

# Conventional CT and MRI

This guideline has defined measurability of lesions on CT scan based on the assumption that CT slice thickness is 5 mm or less. If CT scans have slice thickness greater than 5 mm, the minimum size for a measurable lesion should be twice the slice thickness. MRI is also acceptable in certain situations (e.g. for body scans).

Use of MRI remains a complex issue. MRI has excellent contrast, spatial, and temporal resolution; however, there are many image acquisition variables involved in MRI which greatly impact image quality, lesion conspicuity, and measurement. Furthermore, the availability of MRI is variable globally. As with CT, if an MRI is performed, the technical specifications of the scanning sequences used should be optimized for the evaluation of the type and site of disease. Furthermore, as with CT, the modality used at follow-up must be the same as was used at baseline and the lesions should be measured/assessed on the same pulse sequence. It is beyond the scope of the RECIST guidelines to prescribe specific MRI pulse sequence parameters for all scanners, body parts, and diseases.

Ideally, the same type of scanner should be used and the image acquisition protocol should be followed as closely as possible to prior scans. Body scans should be performed with breath-hold scanning techniques, if possible.

# PET-CT

At present, the low dose or attenuation correction CT portion of a combined PET-CT is not always of optimal diagnostic CT quality for use with RECIST measurements. However, if the site can document that the CT performed as part of a PET-CT is of identical diagnostic quality to a diagnostic CT (with IV and oral contrast), then the CT portion of the PET-CT can be used for RECIST measurements and can be used interchangeably with conventional CT in accurately measuring cancer lesions over time. Note, however, that the PET portion of the CT introduces additional data which may bias an investigator if it is not routinely or serially performed.

# Ultrasound

Ultrasound is not useful in assessment of lesion size and should not be used as a method of measurement. Ultrasound examinations cannot be reproduced in their entirety for independent review at a later date and, because they are operator dependent, it cannot be guaranteed that the same technique and measurements will be taken from one assessment to the next. If new lesions are identified by ultrasound in the course of the study, confirmation by CT or MRI is advised. If there is concern about radiation exposure at CT, MRI may be used instead of CT in selected instances.

# Endoscopy, Laparoscopy

The utilization of these techniques for objective tumor evaluation is not advised. However, such techniques may be useful to confirm complete pathological response when biopsies are obtained or to determine relapse in trials where recurrence following complete response (CR) or surgical resection is an endpoint.

